The only people who will have access to the questionnaire data are study staff. It will be entered by the participant directly into the secure, password protected Survey Monkey™ or redcap program. If the participant is uncomfortable answering the questionnaires, he/she does not have to complete them and can still participate in the remainder of the experimental sessions. In addition, if at any time the participant wishes to stop the experiment, he/she can do so without question and will be compensated for the time completed.

There is minimal risk associated with reporting of Tanner Stage & Pubertal Development Questionnaire. The children may feel embarrassed reporting about the stages of their genital and breast development. In order to minimize this, the experimenter will leave the room while the child completes the questionnaire and they will be given a folder to place the questionnaire into to give back to the experimenter. Furthermore, the Adolescent Risk Questionnaire and Eating Disorder Examination Questionnaire are administered (as with all surveys) are administered in a private room. We make clear in the directions that there are no right or wrong answers and that their responses will be kept confidential. These instruments are not meant to be diagnostic in the manner in which they are being administered and are being used in the context of the research to understand how desire to regulate food intake and engage in various forms of risk behavior and dieting may interact with our study measures to influence weight change over time. See section 14.1 for more discussion on this.

Furthermore, at the end of Visits 10-12 we will hand out a resource sheet which can provide information about how to get help regarding many concerns.

9.4 Describe all drugs and devices used in the research and the purpose of their use, and their regulatory approval status.

Response: n/a

9.5 Describe the source records that will be used to collect data about subjects. (Attach all surveys, scripts, and data collection forms.)

Response: (see above)

9.6 What data will be collected including long-term follow-up.

Response:

Pubertal ratings, self-efficacy, height/weight/body compositions, scarcity ratings, risk taking propensity, impulsivity, child feeding practices and food frequency will all be assessed at visits 6, 7, 8 (6, 15, and 24 month follow up).

Pubertal ratings, self-efficacy, height/weight/body compositions, scarcity ratings, risk taking propensity, impulsivity, child feeding practices, physical activity and sleep will all be assessed at follow up visits 10, 11, 12.

9.7 For HUD uses provide a description of the device, a summary of how you propose to use the device, including a description of any screening procedures, the HUD procedure, and any patient follow-up visits, tests or procedures.

Response: n/a

10.0 Data and Specimen Banking

10.1 If data or specimens will be banked for future use, describe where the data/specimens will be stored, how long they will be stored, how the data/specimens will be accessed, and who will have access to the data/specimens.

Response: Data will be stored for up to 3 years after data collection. No specimens will be collected.

10.2 List the data to be stored or associated with each specimen.

Response: Data will be stored in a password protected database. The data will not contain any identifying information. No information will be removed from the laboratory.

10.3 Describe the procedures to release data or specimens, including: the process to request a release, approvals required for release, who can obtain data or specimens, and the data to be provided with specimens.

Response: n/a

11.0 Data Management

11.1 Describe the data analysis plan, including any statistical procedures.

Response:

Response: The data will be analyzed using SPSS and SYSTAT software once collection is complete.

2 Way ANOVAS with

Inde: Sex and BMI as predictors

Dep: Food reinforcement

Cov: SES

Variables of interest include:

BMI% pre/post

Sex

SES

Food reinforcement pre/post

Other analyses:

Assigned snack food

Self efficacy scores for health eating

11.2 Provide a power analysis.

Response: 3 level Dependent, 2-2level Independents.

Able to detect effect size of 0.25, 0.5, 0.75, 1.00, or 1.25 at alpha 0.05

>90 0.826 0.999 1.000 1.000 1.000

N>90 used to see small/medium to large effects and also have an even number of participants to evenly split recruitment groups (N= 226, 113 male, 113 female)

11.3 Describe the steps that will be taken to secure the data (e.g., training, authorization of access, password protection, encryption, physical controls, certificates of confidentiality, and separation of identifiers and data) during storage, use, and transmission.

Response: The Principal Investigator, [name], will be responsible for ensuring data integrity and safety monitoring for human subjects who are involved in the research by training all staff to abide by appropriate protocols, including data security, password protection, and GRP/CITI training. The project coordinator will monitor these training steps.

All data that are collected by the investigators are stored in password protected databases or in locked filing cabinets, where the information is only associated with a numeric identifier and not a subject's personal information.

11.4 Describe any procedures that will be used for quality control of collected data.

Response: Quality control checks are used for all calculations and manual data inputs. At least two experimenters will check all values via double data entry. Data collected via survey monkey or redcap will be downloaded.

11.5 Describe how data and specimens will be handled study-wide:

Response: Data will be stored in a password protected database. The data will not contain any identifying information. No Information will be removed from the laboratory.

11.6 What information will be included in that data or associated with the specimens?

Response: ID number associated with height and weight data. No specimens collected.

11.7 Where and how data or specimens will be stored?

Response: Data will be stored in a password protected database. The data will not contain any identifying information. No information will be removed from the laboratory.

11.8 How long the data or specimens will be stored?

Response: 3 years

11.9 Who will have access to the data or specimens?

Response: PI, research coordinator, Approved research assistants on the project will have access to the data.

11.10 Who is responsible for receipt or transmission of the data or specimens?

Response: n/a

11.11 How data and specimens will be transported?

Response: n/a

12.0 Provisions to Monitor the Data and Ensure the Safety of Subjects

12.1 Describe the plan to periodically evaluate the data collected regarding both harms and benefits to determine whether subjects remain safe.

Response: *The Principal Investigator, [name], will be responsible for ensuring data integrity and safety monitoring for human subjects who are involved in the research. The project coordinator will bring any concerns or*

comments from the participants or research assistants to the attention of the PI.

This study asks students to answer a variety of surveys asking about their risk taking and eating behaviors. Because the questionnaires used in this study are not meant to be diagnostic and because the measures examine common, subclinical eating behaviors, we do not take any action in children who score high on disordered eating behavior. We lack the qualifications and the authority to perform diagnostic screening. Additionally, because we aim to protect privacy and confidentiality of our participants, we are not willing to share their response information with parents. We have added a notification at the end of the Adolescent Risk Questionnaire which provides contact information for the Crisis Services hotline, so that students may anonymously seek that support if they are interested. Furthermore, we will supply a resource sheet to all participants at the end of visits 10, 11, 12, should they participate in SNAK Part 2.

12.2 *Describe what data are reviewed, including safety data, untoward events, and efficacy data.*

Response: participant comments will be reported

12.3 *Describe how the safety information will be collected (e.g., with case report forms, at study visits, by telephone calls with participants).*

Response: n/a

12.4 *Describe the frequency of data collection, including when safety data collection starts.*

Response: n/a

12.5 *Describe who will review the data.*

Response: n/a

12.6 *Describe the frequency or periodicity of review of cumulative data.*

Response: For the proposed project the data will be reviewed at 1 month and 2 months. For the previously conducted research, approximately every 6 months the data was reviewed by the PI.

12.7 *Describe the statistical tests for analyzing the safety data to determine whether harm is occurring.*

Response: n/a

12.8 Describe any conditions that trigger an immediate suspension of the research.

Response: n/a

13.0 Withdrawal of Subjects

13.1 Describe anticipated circumstances under which subjects will be withdrawn from the research without their consent.

Response: Anyone unable to attend their appointments or a participant that frequently canceled appointments will be withdrawn due to the time-sensitive nature of the data collection. Should they drop out or be withdrawn from the study, they will be asked to answer a 4-5 question exit survey about their experience.

13.2 Describe any procedures for orderly termination.

Response: N/A

13.3 Describe procedures that will be followed when subjects withdraw from the research, including partial withdrawal from procedures with continued data collection.

Response: Anyone that is withdrawn from the study will be paid for their time. They will not be contacted for future data and their data will be coded as a withdraw. Their data will stay on file for the study term, unless they ask for their data to be withdrawn.

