Response: A survey monkey questionnaire “*SNAK Screening Survey 6.25.18.pdf*” will be used to screen all participants. This screening begins with a consent process prior to screening. The online screening (or phone screening when someone discloses that they do not have internet access) inquires about child date of birth, height/weight, liking of study foods, health conditions, allergies, and current use of medications. A participant is not eligible if they are allergic to a critical mass of the study foods, they are on medications effecting their eating.

At the first appointment the child is directly assessed for height, weight, and the linking of study foods. They must like at least one of the health and one of the junk foods 50% or more in order to participate. Additionally the BMI z score must fall into the range of -1.5 to 2.0 in order to stay in the study after Visit 1. For those that qualify at the end of Visit 1, they will not be reassessed for these criteria after Visit 1. Therefore the only exclusion criteria after visit 1 will be ability to schedule and attend study appointments.

3.3 *Indicate specifically whether you will include or exclude each of the following special populations: (You may not include members of these populations as subjects in your research unless you indicate this in your inclusion criteria.)*

- *Adults unable to consent*
- *Individuals who are not yet adults (infants, children, teenagers)*
- *Pregnant women*
- *Prisoners*

Response: Including individuals who are not yet adults.

3.4 *Indicate whether you will include non-English speaking individuals. Provide justification if you will exclude non-English speaking individuals.*

(In order to meet one of the primary ethical principles of equitable selection of subjects, non-English speaking individuals may not be routinely excluded from research. In cases where the research is of therapeutic intent or is designed to investigate areas that would necessarily require certain populations who may not speak English, the researcher is required to make efforts to recruit and include non-English speaking individuals. However, there are studies in which it would be reasonable to limit subjects to those who speak English: e.g., pilot studies, small unfunded studies with validated instruments not available in other languages, numerous questionnaires, and some non-therapeutic studies which offer no direct benefit.)

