To test our primary hypotheses related to zBMI change over time, appointments (level 1) were nested within individuals (level 2) and models included month of visit, sex, DEBQ score, pubertal development score and baseline zBMI as fixed effects. Our dependent measure was zBMI at baseline and 6, 15, and 24 months. We used number of months between visits as our marker of time (i.e. 6, 15, and 24). To test hypotheses related to sensitization, we categorized people as “sensitizers” (> 1) or “satiators” (≤ 1) depending on their change in RRV of food from baseline to post. This threshold was chosen to account for participants who increased responding from baseline to post, even by a small amount, while allowing participants who did not change responding or who decreased responding to be considered together as satiators. To test hypothesis 1, we included HED sensitization in the model and examined interactions with time. To test hypothesis 2, we included LED sensitization in the model and examined interactions with time. To test hypothesis 3, we included both HED and LED sensitization in the model, we interacted each one individually with time, and we interacted them with each other and with time. Finally, to test hypothesis 4, we added DD as a fixed effect and interacted it with HED sensitization and visit to examine moderation.

- 1) Temple, J. L. Factors that influence the reinforcing value of foods and beverages. *Physiol. Behav.* **136**, 97-103, doi:10.1016/j.physbeh.2014.04.037 (2014).
- 2) Clark, E. N., Dewey, A. M. & Temple, J. L. Effects of daily snack food intake on food reinforcement depend on body mass index and energy density. *Am. J. Clin. Nutr.* **91**, 300-308, doi:10.3945/ajcn.2009.28632 (2010).

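### Staff withdrawal for missed or cancelled visits also ends outcome collection, so later zBMI is missing by rule even for children who already have a sensitization score

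*Protocol*

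**What the plan says.** Protocol Section 13.1, answering a question about withdrawal without the subject's consent, names two triggers. One is being unable to attend. The other is frequent cancelling: "a participant that frequently canceled appointments will be withdrawn due to the time-sensitive nature of the data collection". No number of cancellations is given. Section 3.2 is consistent with this: "Therefore the only exclusion criteria after visit 1 will be ability to schedule and attend study appointments".

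The prompt in Section 13.3 asks about partial withdrawal with data collection continuing. The answer offers no such route: "They will not be contacted for future data and their data will be coded as a withdraw". Two things soften the rule. Data already collected are retained ("Their data will stay on file for the study term, unless they ask for their data to be withdrawn"), and Section 13.1 adds that "they will be asked to answer a 4-5 question exit survey about their experience". That survey is not said to include height or weight.

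On the outcome, the SAP states: "Our dependent measure was zBMI at baseline and 6, 15, and 24 months". It fits a multilevel model, with visits nested in individuals, partly to account for missing values. It reports no significant baseline difference between complete and incomplete cases on child and parent BMI, race, sensitization, pubertal development and food insecurity.

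**The concern.** The exposure in H1-H4 is the sensitizer or satiator category, derived from the change in RRV across a two-week snack period. In the Protocol Section 9.2 schedule the first-wave RRV tests for the two foods fall at Visits 2-5. The outcome needs only height and weight, taken at Visits 1, 6, 7 and 8. Visits 6 and 7 include no RRV task. Once a child has a score for at least one food, height and weight are the main thing still needed from that child for the zBMI models.

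Section 13 does not separate the two. Cancelling often ends the tasks and the outcome follow-up together, so the missing zBMI arises from a staff decision and not from refusal. Two things are at stake:

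- **Precision.** H1-H4 are tests of interactions with time, and the late visits carry most of the information on time.
- **Possible selection.** Cancelling may go with household circumstances that also bear on weight gain. The protocol recognises transport as a barrier (Section 15.1 reimburses bus and rail fares) and cites preliminary data linking the child's perceived food scarcity to weight change (Section 14.1). The multilevel model protects only to the extent that missingness is explained by what the model observes.

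**Working it through.** **1. Is there a plan figure to reproduce?** There is none for this rule: no attrition rate, no count of staff withdrawals and no loss allowance is stated. The nearest figures are the enrolment target of 226 (Protocol Section 3.1) and the SAP's requirement of 180 for effect size 0.19, alpha 0.05 and power 0.80. The SAP does not give the scale of 0.19. Read as a correlation, 80% power needs 216 two-sided or 171 one-sided. Read as Cohen's f with two groups, it needs 220. None gives 180, so that figure is not a sound base for a power calculation about withdrawals.

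**2. What one child contributes to a slope.** Inputs are the SAP time points 0, 6, 15 and 24 months. For one child the within-child slope has variance σ²/SS, where SS = Σ(t − t̄)² and σ² is the within-child residual variance.

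- All four visits: t̄ = 45/4 = 11.25. SS = 126.5625 + 27.5625 + 14.0625 + 162.5625 = 330.75.
- Month 24 missing: t̄ = 21/3 = 7. SS = 49 + 1 + 64 = 114, and 114/330.75 = 0.34.
- Months 15 and 24 missing: t̄ = 3. SS = 9 + 9 = 18, and 18/330.75 = 0.05.
- Only baseline present (withdrawn after the RRV visits and before month 6): SS = 0.

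**3. How far these ratios carry into the model.** They apply directly if children share a common slope apart from residual error. The SAP states nesting within individuals but not whether slopes are random. With a random-slope variance τ², a child's weight is 1/(τ² + σ²/SS), and the loss is smaller. As an illustration, assume τ² = σ²/330.75:

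- Without month 24, the relative weight is 2/(1 + 330.75/114) = 2/3.90 = 0.51.
- Without months 15 and 24, it is 2/(1 + 330.75/18) = 2/19.375 = 0.10.

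The figures of 34% and 5% are therefore the low end. The direction does not change.

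**4. Could the loss be informative?** The SAP's check covers five areas. It does not list SES (the covariate in Protocol Section 11.1), DD (the moderator in H4) or DEBQ (a model covariate). SES and food insecurity are not in the SAP's models. A comparison of baseline values cannot detect missingness that depends on later weight gain, and p > 0.05 does not show that the groups are alike. No sensitivity analysis for data missing not at random is described.

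**5. Who could be recovered?** Children withdrawn before they have any sensitization score lack the exposure, and later zBMI would not bring them into H1-H4. A child with a score for one food can enter H1 or H2 but not H3. Families who cannot attend at all cannot come for a weight check. No remote child measurement is described.

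**The case against.** Much of the case on the other side stands. Nothing collected is thrown away, and a withdrawn child with a score and an early zBMI can remain in the model. The SAP did look for differences between complete and incomplete cases and found none significant. The protocol also reschedules for non-compliance and for COVID screening, so withdrawal is for frequent cancelling and not for a single missed visit. After Visit 5 the visits are months apart, except Visits 8 and 9, which leaves limited room for frequent cancelling. The number of children affected may be small.

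A reader might infer more than the documents support in four ways:

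- **That 24-month data are discarded and the number analysed falls.** The later values are not collected. What falls is the count of late zBMI values and the slope information, not necessarily the number of participants in the model.
- **That the drop from 226 to 180 measures the rule.** The difference is 46 (46/226 = 20.4%), but no document calls it expected loss, let alone staff withdrawals. If 0.19 is taken as a two-sided correlation, power is 0.82 at 226 and 0.73 at 180. That contrast rests on an assumed scale under which 180 would not give 80% power in the first place.
- **That the withdrawn are shown to be a selected group.** This is plausible only. Any bias figure would need an invented difference between withdrawn and retained children.
- **That the time-sensitive data are only those of Visits 2-5.** Section 13.1 does not say so. RRV is repeated at Visits 8 and 9, one week apart, and the SAP uses 6, 15 and 24 months as its time marker. A late height and weight measurement is still usable if the actual month is analysed.

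What remains is that the rule ends collection of an outcome that could still be measured, for children whose exposure is known.

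**Conclusion.** The point holds as a cheap, worthwhile improvement to the design. For a child with a sensitization score, Section 13 makes later zBMI missing by staff rule, on a trigger that is not defined. That child's within-child information on the slope falls to 34% of its full value without month 24, to 5% without months 15 and 24, and to nothing if only baseline is present. These percentages assume the SAP's nominal visit times and no random slope; with random slopes the loss is smaller but still there. The loss may be informative, and the SAP's check does not settle this either way. The overall effect on H1-H4, whether as bias or lost power, cannot be computed, because the documents do not say how many children were withdrawn, when or why.

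**What to change.** - Amend Sections 13.1 and 13.3 so that missed or cancelled visits end the RRV and survey tasks but not follow-up, and state what counts as frequent cancelling. Distinguish this clearly from a family withdrawing consent.
- Unless consent is withdrawn, keep inviting every child with a HED or LED sensitization score to height and weight only at 6, 15 and 24 months. Where a visit is late, use the actual month of measurement as time in the model.
- Keep these children in the H1-H4 models. Report withdrawals by reason, timing and sensitization status. Extend the complete-versus-incomplete comparison to SES, DD and DEBQ, and add a sensitivity analysis for data missing not at random.

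The cost is protocol and consent wording and a few short visits by existing staff; the added reporting and analysis need no new data. The change will not recover families who cannot attend, or children withdrawn before they have a sensitization score. If follow-up has already closed, only the reporting and analysis parts can still be done.

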14.0 Risks to Subjects

14.1 List the reasonably foreseeable risks, discomforts, hazards, or inconveniences to the subjects related to the subjects' participation in the research. Include as may be useful for the IRB's consideration, a description of the probability, magnitude, duration, and reversibility of the risks. Consider physical, psychological, social, legal, and economic risks.

Response:

The level of risk encountered by the participants in this experiment is NO GREATER THAN MINIMAL. There are no invasive techniques being used or substances that are potentially harmful. There is a low probability of risks from completing some of our study instruments, including risk of disclosure of information outside the context of the research study. Sub-clinical disordered eating behavior, such as dieting and food restriction, is assessed on our instruments, such as the DEBQ and the EDE-Q. These instruments are not meant to be diagnostic in the manner in which they are being administered and are being used in the context of the research to understand how desire to regulate food intake and engage in various forms of dieting may interact with our study measures to influence weight change over time. These are commonly used measures in this population and are not known to cause physical, psychological, social, legal or economic harm. Food scarcity is being assessed using two instruments in this study (VFS and FIQ). It is critical that we gather information about the child's perceived food scarcity, as we have preliminary data showing that the child's perception is more strongly related to weight change than the parent's perception. The child may feel some embarrassment from answering questions about their food scarcity, but all other risks (physical, social, legal, and economic) remain extremely low probability.

Finally, the participants in our study complete the ARA questionnaire. This questionnaire is modeled from the Youth Behavioral Risk Surveillance study questionnaire which has been used in tens of thousands of adolescents from across the country for over a decade. There are no known or reported risks from the administration of this questionnaire. The participants are told that their answers will be kept confidential, including not being reported to their parents. They are at no legal risk from reporting this activity. It is common for studies of adolescent substance use to provide this type of disclaimer to participants completing questionnaires of this nature in order to encourage honesty and reduced undue concern from the participant that there will be punishment for their answers. We have added a pop up containing contact information about a local mental health hotline (Crisis Services) at the end of the ARA survey, so that any student has access to this confidential line if they are interested. Furthermore, we will supply a resource sheet to all participants at the end of visits 10, 11, 12, should they participate in SNAK Part 2 or 3.

Despite these surveys not being clinical assessments we will attempt to notify parents/guardians of potential ongoing high risk eating behaviors and mental health responses of their teenagers. Data from the EDE-Q and ARA will be reviewed at the end of SNAK Part 2 visits (Visits 10-12). Should responses indicate recent purging behavior, suicidal ideation or attempt, the parent/guardian of the child will be contacted using the "Parental Contact due to EDE or ARA Phone Script" based on the following assessment plan.

The EDE Q survey data will be reviewed by research assistant at the end of SNAK Part 2 (Visits 10, 11, 12). If an individual scores an average > 4.0 globally (average of EDE-Q

items #1-12 and 19-28), and endorses >2 on #16 (vomiting) or >2 on #17 (laxative use), the PI, [name], will call the parent/guardian of the child to suggest they talk to their child about their risky eating habits and consider seeking medical evaluation following the “Parental Contact due to EDE or ARA Phone Script” within one week.

The ARA survey data will be reviewed by research assistant at the end of SNAK Part 2 (Visit 12). Should a participant endorse thoughts of suicide (#15) greater than “once or twice” or any endorsement of “suicide attempt” (#16) in the past 12 months, the PI, [name], will call the parent/guardian of the child to suggest they talk to their child about their mental health and consider seeking medical evaluation following the “Parental Contact due to EDE or ARA Phone Script” within one week.

The “Parental Contact due to EDE or ARA Phone Script” will not specifically disclose the child’s questions or responses, but will convey the nature of the concern as “high risk eating behaviors” or “mental health.” The PI will make 3 documented phone calls attempts to parents over 3 weeks. If no contact is made, the research coordinator will mail a letter using the indicated script and include the “Resource letter” along with it.

Individuals will not be contacted for data from appointments that they have previously consented/assented to. The SNAK Part 2 Consent and Assent forms will include a statement about potential disclosure. Those that have already signed a SNAK Part 2 Consent will be provided a Consent/Accent Addendum notifying them of the change prior to the start of their next scheduled appointment. The child will not be dismissed from the study based on these survey responses.

14.2 If applicable, indicate which procedures may have risks to the subjects that are currently unforeseeable.

Response: n/a

14.3 If applicable, indicate which procedures may have risks to an embryo or fetus should the subject be or become pregnant.

Response: n/a

14.4 If applicable, describe risks to others who are not subjects.

Response: n/a

